of coffee daily. This increases their likelihood of having GERD. In the Middle East, fewer studies have assessed the effect of GERD. A recent cross-sectional study assessed the prevalence of GERD among medical students in Egypt. They found a prevalence of 17.1%. They found an association between increasing stress levels and increasing GERD severity. Also, smoking was a significant risk factor for GERD symptoms. Another cross-sectional study among medical students in 21 universities in Egypt. They reported a prevalence of 28.4%. Again, they found that an increasing level of stress and anxiety was associated with increasing GERD severity. Finally, Two cross-sectional studies were conducted in Saudi Arabia. They reported a prevalence of 23.8% and 23.1% respectively. To our knowledge, no study has assessed the GERD and its related quality of life among medical students in Middle East and linked their findings with eating behaviour

Research Questions

1. What is the prevalence of GERD among medical students and interns, its risk factors, its impact on health-related quality of life, and psychological disturbance?
2. What is the impact of eating behavior on GERD prevalence?

Aim

To improve the quality of life among medical students and interns in the Middle East countries

Objectives

1. To assess the prevalence of GERD among medical students and interns in the Middle East
2. To assess the effect of GERD on health-related quality of life
3. To assess the associated risk factors of GERD
4. To assess the impact of eating behavior on GERD prevalence
5. To assess the impact of stress, anxiety, and depression on increasing GERD prevalence

Methodology

Technical design

1. **Study design:** Cross-sectional study

2. **Setting:** Medical students in some Middle East countries (Egypt, Sudan, Somalia, Libya, Morocco, United Arab Emirates, Jordan, Saudi Arabia, Yemen, Iraq, and Palestine)
3. **Time:** From August 2025 to December 2025
4. **Population:** Arabic Medical students and interns in the MEAN region

5. Inclusion Criteria

- Medical students and interns studying medicine in the Middle East countries
- Have access to online platforms

6. Exclusion Criteria

- Students or interns who refused to participate

7. Sampling

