We calculated the total sample size using Epi Info version 7.2.60(Epi InfoTM | CDC, n.d.) Assuming a 28.4% (Essa et al., 2024) prevalence rate and a 5% error margin with a 95% confidence interval, the sample size required for each country is 312. After adding a 10% nonresponse rate, the final sample size is about 343 for each country, so the total sample size will be 3773

8. Sampling Technique: Convenience Sampling

Operational design

1. **Pilot:** We will perform a pilot study in each country before starting the study to assess the readiness of the questions and the reliability of the questions via the Cronbach's alpha test.
2. **Study field:** an online questionnaire will be shared via an online platform with the target population.

3. Data collection method

An online questionnaire will be shared via social media platforms, including Facebook, WhatsApp, and Telegram.

The questionnaire consists of 6 sections

- The first section discusses the importance of the study for the participants, informing them that their data will be used only for research purposes, and obtaining informed consent
- The second section asks about the sociodemographic data and associated risk factors such as age, sex, residency, GPA, smoking, BMI, and eating habits
- The third section contains the GERDQ questionnaire(Jones et al., 2009). It is composed of 6 Likert scale questions that ask about GERD symptoms such as heartburn, nausea, and regurgitation. Each question has 4 answers scored from 0 to 3, making a rank from 0 to 18. If the participant scores 8 or more, this diagnoses GERD. Furthermore, the symptoms severity can be assessed. A score of 0-2 makes 0 % of having GERD, 3-7 makes a 50% likelihood of having GERD, 8-10 makes a 79% and 11-18 makes a 89% of having GERD. This questionnaire has a sensitivity being 65% and a specificity being 71% to diagnose GERD
- The Fourth section asks about the quality of life for GERD patients. We used the GERD-HRQL(Velanovich, 2007). This is a 16 Likert scale questionnaire that asks about the effect of GERD symptoms on the quality of life. The first 15 questions had 6 answers, ranging from no symptoms to Symptoms that are incapacitating – unable to do daily activities. This score ranges from 0 to 75. The sixteenth question asks about the present condition. The quality of life is calculated via the first 15 questions (scores from 0 to 75), with higher scores indicating lower quality of life.

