- The fifth section asks about eating behavior. We used the Dutch Eating Behavior Questionnaire (DEBQ)(van Strien et al., 1986). This is a 33 Likert scale questionnaire that assesses the eating behavior in three items (retained eating, emotional eating, and External eating). Each question is composed of 5 answers (from never to very often) and scores range from 1 to 5.

- The final section asks about stress, anxiety, and depression using the DASS-21(Lovibond & Lovibond, 2015) questionnaire. This is composed of 21 Likert scale questions, each had 4 answers scored from 0 to 3. The scale is divided into 3 sections to assess depression, stress, and anxiety. The cumulative score for each part will be multiplied by two for interpretation of the severity of each section.
 1. For the Depression score, 0-9 indicates a normal person, 10-13 indicates mild symptoms, 14-20 indicates moderate, 21-27 indicates severe symptoms, and 28+ indicates extremely severe symptoms.
 2. For anxiety scores, 0-7 indicates a normal person, and (8-9), (10-14), (15-19), and 20+ indicate mild, moderate, severe, and extremely severe levels of anxiety.
 3. For stress scores, 0-14 indicates a normal person. A score of (15-18), (19-25), 26-33), and 34+ indicate a mild, moderate, severe, and extremely severe levels of stress.

4. Statistical analysis

First, data will be summarized according to its type. Categorical data will be summarized using frequency and percentage. Continuous data will be tested for normality. If the data is normally distributed, we will summarize it using mean and SD, and if not, median and IQR will be used. We will assess the difference between the population according to their sociodemographic data using a Chi-square and a Mann-Whitney U test. A p-value of <0.05 will be used as a cutoff point for statistically significant results. We will assess the correlation between all continuous data (GERD, GERD-HRQL, DEBQ, and DASS-21). Finally, a multiple linear regression test will be used to assess the relationship between the assessed variables.

Administrative design

1. Ethical consideration

- The study protocol will be approved by the Institutional Review Board of Zagazig University, Faculty of Medicine
- Study participants will be included after informed consent.

2. Confidentiality and data retention

Data collected will be kept confidential.

3. Risks and benefits of the participants

There is no cost for this study

Results

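### The analysis and the per-country precision treat respondents as independent although they are nested in medical schools; the effect is modest for most listed factors, and cheap to prevent before data collection

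*Combined protocol and SAP*

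**What the plan says.** Under Operational design, item 4 (Statistical analysis), sociodemographic comparisons are made "according to their sociodemographic data using a Chi-square and a Mann-Whitney U test". The scores for GERD, quality of life, eating behaviour and psychological distress are then correlated with one another, and finally "a multiple linear regression test will be used to assess the relationship between the assessed variables". The decision rule is: "A p-value of <0.05 will be used as a cutoff point for statistically significant results". No random effect, cluster-robust variance, design effect, or country or school term is mentioned.

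Under Technical design, the population is "Medical students and interns studying medicine in the Middle East countries", drawn from 11 countries. The technique is stated as "Sampling Technique: Convenience Sampling", and on recruitment the plan says: "An online questionnaire will be shared via social media platforms, including Facebook, WhatsApp, and Telegram". The sample size is 312 per country for a margin of 5 points around 28.4%, raised to 343 for nonresponse, or 3773 in total. The second section of the questionnaire gives as examples "age, sex, residency, GPA, smoking, BMI, and eating habits". Medical school is not among them.

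**The concern.** Every respondent belongs to a teaching institution. The authors know the multi-school structure: the Rationale describes an Egyptian student survey across 21 universities with a prevalence of 28.4%, the figure used for planning. Students at one school may share timetable, examinations and surroundings, so their reflux, stress and eating scores may be correlated. If so, unadjusted standard errors are too small for any factor that also clusters by school, and for prevalence itself.

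Two results are exposed: objective 3 (risk factors), where p-values would not have their stated 5% error rate, and objective 1 (prevalence), where the country intervals would be too narrow. A country term would not settle this. It removes differences between country averages and leaves correlation among students of one school inside a country. If school is not recorded, a school-level adjustment cannot be made afterwards.

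**Working it through.** **1. The plan's own figure.** With p = 0.284, margin d = 0.05 and z = 1.96:

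n = z² p(1−p)/d² = 312.46, stated as 312. Then 312 × 1.10 = 343.2, stated as 343, and 343 × 11 = 3773.

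All three figures reproduce with a design effect of 1, so the sample size contains no hidden allowance for clustering.

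**2. Assumptions.** The documents give no ICC and no number of schools. Assumed: 5, 10 or 20 schools per country, hence m = 343/5 = 68.6, 343/10 = 34.3 or 343/20 = 17.15 respondents per school, and an outcome ICC of 0.01 to 0.05 within a country. The test is taken as two-sided.

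**3. Formulas.** Let ICC_x be the factor's own intra-school correlation, equal to 1 if it is constant within schools.

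- Design effect: D = 1 + (m−1) × ICC × ICC_x
- True error rate of a nominal 5% test: 2 × [1 − Φ(1.96/√D)]
- Margin for country prevalence: 5 × √D, with ICC_x = 1

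**4. Results.**

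| Schools per country | ICC | D, constant factor | Error, constant factor | D, ICC_x = 0.20 | Error, ICC_x = 0.20 | Prevalence margin (points) |
|---|---|---|---|---|---|---|
| 20 | 0.01 | 1.16 | 6.9% | 1.03 | 5.4% | ±5.4 |
| 20 | 0.05 | 1.81 | 14.5% | 1.16 | 6.9% | ±6.7 |
| 10 | 0.01 | 1.33 | 9.0% | 1.07 | 5.8% | ±5.8 |
| 10 | 0.02 | 1.67 | 12.9% | 1.13 | 6.6% | ±6.5 |
| 10 | 0.05 | 2.67 | 23.0% | 1.33 | 9.0% | ±8.2 |
| 5 | 0.01 | 1.68 | 13.0% | 1.14 | 6.6% | ±6.5 |
| 5 | 0.05 | 4.38 | 34.9% | 1.68 | 13.0% | ±10.5 |

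Worked example, 5 schools and ICC 0.05: for ICC_x = 0.20, D = 1 + 67.6 × 0.05 × 0.20 = 1.676 and the error rate is 2 × [1 − Φ(1.96/1.295)] = 13.0%. For prevalence, D = 1 + 67.6 × 0.05 = 4.38 and the margin is 5 × √4.38 = 10.5 points.

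The margin of 5 points belongs to 312 completers, while m above uses 343. With 312 throughout, m = 15.6 to 62.4 and D = 1.146 to 4.07, so the margin is 5 × √1.146 = 5.4 to 5 × √4.07 = 10.1 points. The conclusion does not change.

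**5. Simulation of the Chi-square test under a true null** (prevalence 28.4%):

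- Factor varying fully within schools: 4.2% to 5.6% rejections over ICC 0.01 to 0.05 and 10 to 62 respondents per school.
- 110 schools of 34, ICC 0.05: about 9% for a factor with ICC_x = 0.20 and 22% for a school-constant factor. With unequal school sizes, about 13% and 35% to 36%.
- School-clustered standard errors over 110 pooled schools: about 4.5% to 6.3%.
- School-clustered standard errors with only about 10 schools: about 8% to 11%, so ordinary clustering is not enough there.

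**The case against.** - **Size for the listed factors.** None of the named items is shown to be constant within a school, and residency, the likeliest candidate, is not defined. A reader might infer that the risk-factor tests run at error rates of 20% to 35%. The documents do not support that: such rates need a school-constant factor as well as high assumed ICCs or few schools. This objection stands and sets the priority.
- **Most objectives are little affected.** Objectives 2, 4 and 5 rest on individual scores, which probably vary mostly within schools. For a factor deliberately balanced within schools, the plain Chi-square was slightly conservative (3.8% rejections). Standard errors are therefore not too small for every factor.
- **Everything numerical is assumed.** This is true. With an ICC of zero, or very few respondents per school, the effect disappears. But without a school identifier the study could not show that.
- **Recruitment through shared groups is an inference.** The plan names platforms, not groups, and does not sample by school. A reader might infer that group forwarding creates the clusters, but the text does not say so. The nesting follows from the population alone.
- **School may already be collected.** The item list is given as examples, and country is missing from it although the per-country target needs it. So the text does not prove that school goes unrecorded. Even if it is collected, the analysis section makes no use of it.
- **Selection bias matters more.** Probably so in an open-link convenience sample, and clustered errors do not touch it. The two problems are separate.

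**Conclusion.** The omission is certain: neither the planned tests nor the sample size allows for nesting in schools. Its size is uncertain. For risk factors the probable consequence is modest, most likely at the lower end of the 5% to 13% range unless a factor is strongly shared within schools. For country prevalence the loss does not depend on the type of factor, and the stated precision would be optimistic by between 0.4 and 5.5 points. All of this rests on the assumed 5 to 20 schools per country, ICC 0.01 to 0.05 and factor ICC 0.20; none of these comes from the documents. Separation from country effects is reasoned rather than simulated, because the simulations had no country level. Priority is minor to moderate: the effect is limited, but the remedy is cheap and is lost if school is not recorded.

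**What to change.** 1. **Questionnaire, second section.** Unless it is already collected, make medical school a required item. For interns, specify either the school of graduation or the training institution.
2. **Statistical analysis.** Use a Rao-Scott Chi-square for categorical comparisons. Use school-clustered standard errors for the pooled regression, for correlations (expressed as regression slopes) and for prevalence intervals, alongside a country term. Compare continuous scores between groups by the same clustered regression, because the standard Mann-Whitney test makes no allowance for clustering.
3. **Single-country analyses with few schools.** Add a small-sample correction, for example a t reference with schools minus 1 degrees of freedom, or a wild cluster bootstrap.
4. **Reporting.** Give the number of schools, respondents per school and the estimated ICC.

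Cost: one item and a few lines of analysis text. Some p-values and intervals become less favourable. Respondents become slightly more identifiable, so school-level results should not be published. The report should state that the adjustment corrects standard errors only and not the selection bias of convenience sampling.

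### Objectives 4 and 5 ask about GERD prevalence, but the only multivariable method is a linear regression with no named outcome, so no adjusted estimate for case status is specified

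*Combined protocol and SAP*

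**What the plan says.** Under Objectives, items 4 and 5 take the prevalence of GERD as the outcome. The exposures are eating behaviour (item 4) and stress, anxiety and depression (item 5). Research question 2 repeats the prevalence wording for eating behaviour. Objective 3 asks about risk factors of GERD without naming prevalence.

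Operational design, 3. Data collection method, sets the case definition on the 0 to 18 GerdQ score: "If the participant scores 8 or more, this diagnoses GERD". It then adds: "Furthermore, the symptoms severity can be assessed". On accuracy it states: "This questionnaire has a sensitivity being 65% and a specificity being 71% to diagnose GERD". The available covariates are described as follows: "The second section asks about the sociodemographic data and associated risk factors such as age, sex, residency, GPA, smoking, BMI, and eating habits".

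Operational design, 4. Statistical analysis, contains three inferential sentences:
- Group comparisons: "We will assess the difference between the population according to their sociodemographic data using a Chi-square and a Mann-Whitney U test".
- Correlations: "We will assess the correlation between all continuous data (GERD, GERD-HRQL, DEBQ, and DASS-21".
- Multivariable analysis: "Finally, a multiple linear regression test will be used to assess the relationship between the assessed variables".

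No model for a binary outcome, and no odds ratio or prevalence ratio, appears anywhere. The Results section adds only a general reference to standard methods.

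**The concern.** The outcome in objectives 4 and 5 is a proportion of students above a cut-off, while the analysis section handles GERD as a score. The two can be reconciled only if the plan says which is the dependent variable, and it does not. The group tests are tied to sociodemographic data rather than to DEBQ or DASS-21, and they are unadjusted on any reading.

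Two things are at stake. First, the prevalence questions have no pre-specified adjusted answer. Secondly, the outcome (score or case status) and the adjustment set for objectives 3 to 5 could be settled after the data are seen, against a p-value threshold of 0.05. Adjustment matters here by the protocol's own account: the Introduction suggests that the link between depression and GERD may run through changed eating, so the exposures of objectives 4 and 5 are entangled.

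**Working it through.** **Step 1: the plan's own figure.** Sampling assumes a 28.4% prevalence with a 5% margin. The single-proportion formula gives 1.96² × 0.284 × 0.716 / 0.05² = 312.5, which matches the stated 312. Then 312 × 1.10 = 343.2, and 343 × 11 countries = 3,773, in line with "the final sample size is about 343 for each country, so the total sample size will be 3773". The sample size therefore treats GERD as a binary outcome.

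**Step 2: outcome against method.**
- Objective 4: prevalence by DEBQ. Specified: correlation of scores, and a linear regression with no named outcome.
- Objective 5: prevalence by DASS-21. Specified: the same.
- Objective 3: risk factors of GERD. A regression of the GerdQ score could answer this as severity, so what is missing is only the named outcome and covariates.
- Objective 2: GERD-HRQL, scored 0 to 75. Linear regression suits it.

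**Step 3: does a score slope determine a prevalence ratio?** This is a constructed example; the score distributions are assumed and do not come from the documents. Let 71.6% of unexposed students score evenly over 0 to 6 (mean 3) and 28.4% evenly over 8 to 17 (mean 12.5).
- Exposure A adds one point to every low scorer, so none reaches 8. Slope = 0.716 × 1 = 0.716 points. Prevalence is 28.4% in both groups, ratio 1.00.
- Exposure B moves 7.55% of students from the low to the high group. Slope = 0.0755 × (12.5 − 3) = 0.717 points. Prevalence is 28.4% v 35.95%, ratio 0.3595 / 0.284 = 1.27.

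Nearly equal slopes thus fit either no association with prevalence or a clear one. The example shows what is possible; it does not predict this study's data.

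**Step 4: can the data support a case-status model?** The inputs are 312 × 11 = 3,432 or 3,773 respondents, and the lowest and highest student prevalences in the Rationale.
- 3,432 × 0.171 = 587; 3,432 × 0.284 = 975.
- 3,773 × 0.171 = 645; 3,773 × 0.284 = 1,072.
- If specificity is 71%, the screen-positive rate is at least 1 − 0.71 = 29%, giving 0.29 × 3,432 = 995 or 0.29 × 3,773 = 1,094.

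The two sets of counts cannot both describe GerdQ-positive students. The lower set is the cautious one. Parameters, assuming one each for age, sex, residency, GPA, smoking and BMI, and five for eating habits:
- Objective 5 main model: 10 country + 5 + 3 DASS-21 = 18; 587 / 18 = 32.6 cases per parameter.
- Objective 4 main model: 10 + 5 + 3 DEBQ + 3 DASS-21 = 21; 587 / 21 = 28.0.
- Either second model: 27; 587 / 27 = 21.7.

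If only six countries reached 312, there would be 1,872 × 0.171 = 320 cases. The objective 4 main model would have 5 + 5 + 3 + 3 = 16 parameters, and 320 / 16 = 20.

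**Step 5: effect of imperfect classification.** Screen-positive rate = 0.65p + 0.29(1 − p). For assumed true prevalences of 20% v 40% (ratio 2.0), this gives 0.362 v 0.434, ratio 1.20, if accuracy is the same in both groups.

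**The case against.** The best defence is that the GerdQ score is the intended outcome. The plan lists GERD as continuous, says the score also grades severity, and attaches GERD likelihoods of 0%, 50%, 79% and 89% to score bands. A score regression is therefore relevant to GERD and keeps information that a cut-off discards. This stands for severity and for objective 3. It does not turn a slope in points into an association with prevalence, and the plan never says that the score is the dependent variable.

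A second defence is that linear regression of a 0/1 status would give adjusted prevalence differences, and nothing in the text rules it out. That is correct, and it limits the claim: the plan leaves the case-status estimate unspecified rather than excluding it. It also confirms that the dependent variable has to be named.

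A third is that the objectives request neither adjustment nor a ratio. That is true of their wording, but the plan itself chose multiple regression and collects covariates. Logistic or modified Poisson regression, and the covariate split proposed here, are reasonable choices and not the only valid ones.

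A reader might also infer the size of the problem by treating 17.1% and 28.4% as an exposed and an unexposed group and converting the gap into score points. The documents do not support this. The Rationale gives these as prevalences from two separate Egyptian studies, and the protocol does not say that either used the GerdQ cut-off. Both also lie below the 29% floor implied by the stated specificity.

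**Conclusion.** The concern holds as a gap in specification. Objectives 4 and 5 have a binary outcome by the protocol's own definition, and the only multivariable method names no outcome, covariates or effect measure. Its natural reading gives slopes in score points.

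A reader might go further and conclude that the plan misapplies linear regression to a binary outcome, or that objectives 3 to 5 cannot be answered at all. The text supports neither: it does not say that case status is the linear outcome, and a score model can serve objective 3.

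No numerical bias can be derived from the documents. Step 3 rests on assumed distributions and shows only that a slope leaves the prevalence ratio open. That a case-status model is affordable is an approximate statement. It depends on recruitment reaching target and on the assumed parameter counts, but the margin is comfortable. The prevalence estimate of objective 1 and the data collection are unaffected. The plan should be changed before analysis begins.

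**What to change.** In Operational design, 4. Statistical analysis:
- Add a multivariable logistic or modified Poisson regression (log link, robust standard errors) of GerdQ 8 or more as the main analysis for objectives 4 and 5. Report adjusted odds ratios or prevalence ratios with 95% confidence intervals.
- Exposures: the three DEBQ subscales for objective 4 and the three DASS-21 subscales for objective 5.
- Adjust both for country, age, sex, residency, GPA and smoking. Country is implied by the per-country samples but is not among the example items listed, so confirm that it is recorded.
- Include DASS-21 in the objective 4 model as a candidate confounder, since the Introduction suggests that mood may act through eating behaviour.
- Put possible pathway variables in a second model: DEBQ, BMI and eating habits for objective 5; BMI and eating habits for objective 4.
- For objective 3, name the outcome and covariates.
- Keep linear regression for GERD-HRQL (objective 2) and for the GerdQ score as a secondary severity analysis.
- Word results as associations with screen-positive status, and state that they may be attenuated given the quoted sensitivity and specificity.

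The cost is plan wording and slightly more analysis. No extra participants are needed, and no extra questions if country is recorded. Dichotomising loses some information, which keeping the score model offsets.

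### The only adjusted analysis is ordinary linear regression with no provision for unequal residual variance; for GERD-HRQL its 95% intervals may be too narrow, and robust standard errors would guard against this

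*Combined protocol and SAP*

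**What the plan says.** All of the relevant text is under Operational design, in items 3 (Data collection method) and 4 (Statistical analysis).

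- **Normality.** Continuous data are tested for normality, and the result decides only how they are described: "If the data is normally distributed, we will summarize it using mean and SD, and if not, median and IQR will be used".
- **Adjusted analysis.** The last step is that "a multiple linear regression test will be used to assess the relationship between the assessed variables". No outcome, covariate list, residual check, robust standard error, transformation or fallback model is stated.
- **Threshold.** "A p-value of <0.05 will be used as a cutoff point for statistically significant results".
- **Scores.** GERDQ runs from 0 to 18, with 8 or more counted as GERD. For GERD-HRQL, "The quality of life is calculated via the first 15 questions (scores from 0 to 75"). DASS-21 supplies separate depression, anxiety and stress scores.
- **Expected associations.** The Rationale cites two Egyptian student surveys. In one, GERD severity rose with stress; in the other, with stress and anxiety.

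**The concern.** Default linear-regression standard errors assume that residuals have the same variance at every value of the predictors. A symptom score bounded at zero often breaks that assumption: respondents with a low expected score have little room to vary, and those with a high one have much more. If a predictor truly shifts the mean, the variance then shifts with it.

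Two results could mislead. The interval for the predictor that matters could be too narrow. Also, a predictor with no effect of its own could fall below p = 0.05 too often if it is correlated with the one that matters. The second is relevant here because depression, anxiety and stress are measured together, and a natural conclusion to report is which of them is independently associated with symptom burden. No other adjusted analysis is planned that would act as a check.

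**Working it through.** **1. The plan's own figure.** The Sampling item assumes a 28.4% "prevalence rate and a 5% error margin with a 95% confidence interval". From n = z²p(1−p)/d²: 1.96² × 0.284 × 0.716 / 0.05² = 312.5, against "the sample size required for each country is 312". Then 312 × 1.10 = 343.2 and 343 × 11 countries = 3,773, against "After adding a 10% nonresponse rate, the final sample size is about 343 for each country, so the total sample size will be 3773". The figures reproduce. Without the nonresponse allowance, 312 × 11 = 3,432. The sizes relevant to a regression are therefore about 312-343 (one country) and 3,432-3,773 (all countries).

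**2. When default standard errors fail.** Let r_i be a predictor after removing what the other predictors explain, and σ_i² the residual variance for respondent i.

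- True variance of the coefficient: Σ r_i²σ_i² / (Σ r_i²)².
- Default formula: mean(σ²) / Σ r_i².

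The default is too small when r_i² and σ_i² rise together. That can happen for a skewed predictor with a real effect, and for a null predictor whose spread is greater where the active one is high. It does not happen for an independent null predictor, or when there is no association to make σ² vary.

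**3. Inputs the documents do not give.** No SD, skewness, floor share or correlation between scores is stated. All distributions below are assumptions.

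**4. Simulated coverage of nominal 95% intervals.**

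| Assumed setting | n | Ordinary | HC3 |
|---|---|---|---|
| 0-75 score, no association, 42-82% at zero | 312; 3,432 | 93.7-96.0% | see step 6 |
| 0-75 score, real stress effect, 23-70% at zero: stress | 312; 3,432 | 71-88% | 90-94%; 94-95% |
| 0-75 overdispersed count, three scores correlated 0.6: active predictor | 3,773 | 82-89% | 94-96% |
| Same: correlated nulls | 3,773 | 91-93% | 94-96% |
| As above, correlations 0.6-0.7, 11-39% at zero: active predictor | 3,773 | 77-83% | 94-96% |
| Same: correlated nulls | 3,773 | 87-91% | 94-96% |
| Same, but nulls uncorrelated with the active predictor | 3,773 | 95-96% | not reported |
| Further 0-75 run: active predictor | 343; 1,000; 3,432 | 80-82% | 93-96% |
| Same: correlated nulls | 343; 1,000; 3,432 | 87-90% | 93-96% |
| 0-18 score, overdispersed count capped at 18: active predictor | 3,773 | 89-94% | 94-96% (one of two runs) |
| Same: correlated nulls | 3,773 | 92-95% | 94-96% (one of two runs) |
| 0-18 score, bounded models | 312; 3,432 | 93-96% | 94-96% |

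Each cell used 800 to 3,000 replicates where the number is recorded. With 800, the Monte Carlo error at 95% coverage is √(0.95 × 0.05 / 800) = 0.8 percentage points.

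**5. Arithmetic cross-check.** If the true SD is k times the reported standard error, coverage is 2Φ(1.96/k) − 1. In the run at n = 3,773 with correlation 0.6, the largest k was 1.44 for the active predictor and 1.16 for the nulls.

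- k = 1.44: 2Φ(1.361) − 1 = 82.7%, matching the observed low of 82%.
- k = 1.16: 2Φ(1.690) − 1 = 90.9%, matching the observed low of 91%, a type I error of about 9%.

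In reverse, 71-89% coverage corresponds to standard errors too small by a factor of 1.96/1.058 = 1.85 down to 1.96/1.598 = 1.23. For 87-93%, the factor is 1.96/1.514 = 1.29 down to 1.96/1.812 = 1.08.

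**6. Type I error and the limits of HC3.** With no association, the stress score was rejected in 4.4-5.5% of replicates. With a real stress effect, an independent null covariate was rejected in 4.2-5.8%. Only correlated nulls were affected, at 7-13% (one minus their coverage). In the no-association setting at n = 312, HC3 covered 88-92% for a 15%-prevalence smoking indicator, against 95-96% for ordinary intervals. At n = 3,432 the two were alike (about 94%).

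**The case against.** The strongest opposing case has five parts.

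- **Linear regression does not need a normal outcome.** This stands. With no association, ordinary intervals kept close to nominal coverage even with 82% of scores at zero.
- **A pile-up at zero is not documented.** This stands. The Rationale says of one survey, "They reported a prevalence of 28.4"%, so about 72% would score below 8 on GERDQ, but that is not a share at zero. Beta-binomial scores fitted to exactly 28.4% at 8 or more put anywhere from 0.2% to 22% at zero, depending on the assumed spread.
- **Objectives 3 to 5 concern GERD, measured by GERDQ, where the effect is small or absent.** This largely stands. The larger effect belongs to GERD-HRQL, which serves objective 2, and the plan does not say which score the regression will take as its outcome.
- **GERD-HRQL may be analysed only in respondents with GERD.** The data-collection item is unclear on this. At 28.4% of 3,773 that leaves about 1,070. It does not remove the problem: at n = 1,000 ordinary coverage was still 80-82% for the active predictor and 87-90% for correlated nulls.
- **The same sentence has other gaps.** It plans no binary-outcome model for GERD prevalence and no term for country. This is true, and HC3 addresses neither, but those are separate points.

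**Conclusion.** The point holds in a conditional form and is worth acting on before analysis. If residual variance rises with the mean and a real association exists, ordinary 95% intervals for GERD-HRQL can be materially too narrow: about 71-89% coverage for the active predictor and 87-93% for correlated null predictors, at one-country or full size. For GERDQ the range is about 89-96%. These figures rest on assumed distributions, a mean model that is about right, skewed predictors and, for the null predictors, correlations of 0.6-0.7 between scores.

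A reader might infer three stronger things that the documents do not support.

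- **That the adjusted p-values will be too optimistic.** They may be, depending on the data; skewness or a floor alone does not make them so.
- **That the plan contradicts itself by testing normality and then fitting a linear model.** The check governs descriptive summaries only, the Mann-Whitney test is named without condition, and reporting a median is compatible with linear regression. Normality is in any case not the assumption at issue.
- **That the scores are known to be floor-heavy.** No passage says so.

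**What to change.** Add to item 4, Statistical analysis: *All linear regressions will use heteroscedasticity-robust (HC3) standard errors for p-values and 95% confidence intervals, whatever the normality check shows.* A negative binomial or proportional-odds model for GERD-HRQL can be named as an optional sensitivity analysis.

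The cost is one sentence and one software option. The document is dated 5 August 2025 and collection runs to December 2025, so the change can be fixed in advance. Some intervals will become a little wider. At full size HC3 was close to nominal in the simulations. In single-country models it may fall short of 95%, especially for an uncommon binary predictor, so adjusted conclusions are better drawn from the pooled data.
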